7.1.2. Adverse Events of Special Interest

The following AEs are considered as the adverse events of special interest (AESI), and will be summarized by AESI Category and PT:

Table 3: Adverse Events of Special Interest (AESI)

| AESI Category | Definition |
|---|--|
| Potentialization of aminoglycoside renal toxicity | 
• SMQ: Acute renal failure (Narrow and Broad), and;• Concomitant medication using the WHODD ATC code J01G |
| Long-term cardiovascular effects including changes in lipid profile | 
• SMQ: Dyslipidaemia (Narrow), or;• SOC: Cardiac disorders |
| Hypertension with use of concomitant systemic corticosteroids | 
• SMQ: Hypertension (Narrow and Broad), and;• Concomitant medication using the WHODD ATC code H02A |
| Renal toxicity | 
• SMQ: Acute renal failure (Narrow and Broad) |
| Hepatic toxicity | 
• SOC: Hepatobiliary disorders, or;• HLGT: Hepatobiliary Investigations |
| Malignancies in general | 
• SOC: Neoplasms benign, malignant and unspecified (incl cysts and polyps) |

For potentialization of aminoglycoside renal toxicity and hypertension with use of concomitant systemic corticosteroids, the concomitant medications are those started prior to the onset of corresponding AE.
Abbreviation: AESI = adverse event of special interest; SMQ = Standardized MedDRA Query; ATC = Anatomical Therapeutic Chemical; SOC = System Organ Class; HLGT = High Level Group Term; WHODD = World Health Organization Drug Dictionary

7.2. Clinical Laboratory

Mean and mean change from baseline in clinical laboratory data from central laboratory (including parameters for assessment of hepatic and renal monitoring) listed in [Table 4](#) will be summarized by analysis visit, as well as the last assessment during the on-ataluren treatment period. In addition, shift tables for each laboratory parameters from on-ataluren baseline to each of the post-baseline visit will be provided.

Table 4: Clinical Laboratory Parameters

| Type | Parameters |
|--------------|--|
| Hematology | leukocytes, basophils, basophils/leukocytes, eosinophils, eosinophils/leukocytes, lymphocytes, lymphocytes/leukocytes, monocytes, monocytes/leukocytes, neutrophils, neutrophils/leukocytes, hemoglobin, hematocrit, erythrocytes, platelets |
| Biochemistry | sodium, potassium, bicarbonate, blood urea nitrogen, creatinine, magnesium, calcium, uric acid, glucose, total protein, bilirubin (direct and indirect), aspartate aminotransferase, alanine Aminotransferase, gamma glutamyl Transferase, creatine kinase, alkaline phosphatase, total cholesterol, lactate dehydrogenase (LDH), high-density lipoprotein (HDL), low-density lipoprotein (LDL), triglycerides, and cystatin C |
| Urinalysis | pH, glucose, ketones, blood, protein |

All post-baseline clinical laboratory results will be graded according to CTCAE severity grade (criteria in [Appendix 3](#)), when applicable. For parameters graded according to CTCAE severity, the CTCAE grades increase from baseline to Grade 2 or higher grade will be considered as clinically significant (CS) and the incidence will be summarized for as-treated-OL population.

The incidence of all post-baseline specific renal laboratory parameters provides information on action to be taken for study drug will be summarized.

Table 5: Renal Monitoring Parameters and Actions to Be Taken

| Laboratory Parameter | Stop Study Drug Immediately, Confirm Abnormal Value, and Then Start Work-Up | Stop Study Drug After Confirming ^a Abnormal Value, and Then Start Work-Up |
|----------------------|---|--|
| Serum cystatin C | >2.00 mg/L | >1.33 – 2.00 mg/L |
| Serum creatinine | ≥ Grade 2 (≥1.5 x ULN for age) | Grade 1 (>ULN – 1.5 x ULN for age) |
| Serum BUN | ≥3.0 x ULN | ≥1.5 – 3.0 x ULN |

^a Laboratory abnormalities may be confirmed immediately or at the next scheduled clinic visit based on investigator judgment.

Abbreviations: BUN = blood urea nitrogen, ULN = upper limit of normal

Laboratory abnormality related to elevated liver function test will also be summarized for all post-baseline assessments according to [Table 6](#).

Table 6: Criteria for Elevated Liver Function Test

| Category | Criteria |
|-------------------------------|---|
| Elevated Aminotransferases | 
 ALT >3xULN AST >3xULN ALT or AST >3xULN |
| Elevated Bilirubin | 
 Total Bilirubin >2xULN AST or ALT >3xULN and Total Bilirubin >2xULN |
| Elevated Alkaline Phosphatase | 
 AP >1.5xULN AST or ALT >3xULN, Total Bilirubin >2xULN, and AP >1.5xULN |

Abbreviations: ALT = alanine aminotransferase; AST = aspartate aminotransferase; AP = alkaline phosphatase; ULN = upper limit of normal.

A listing of all CS abnormal laboratory values, renal laboratory abnormal values, and elevated liver function test will be provided.

7.3. Electrocardiogram/Echocardiogram

Overall interpretation of ECG data, including normal, abnormal and clinically significant, abnormal and not clinically significant will be summarized descriptively by the number and percentages of subjects at each analysis visit, and the last assessment during the on-ataluren period.

A listing of all abnormal values for ECG will be provided.

Echocardiogram (left ventricle ejection fraction and sphericity index) will be summarized descriptively, including change from on-ataluren baseline by analysis visit, and the last assessment during the on-ataluren period. Overall interpretation of echocardiogram (normal, abnormal) will be summarized descriptively by the number and percentage of subjects at each visit, and the last assessment during the on-ataluren period.

7.4. Physical Examination

Physical examination results will be listed in subject listings only.

7.5. Vital Signs

Height, weight, and vital signs data will be summarized descriptively, including change from on-ataluren baseline by analysis visit and last assessment during on-ataluren period. A summary will also be provided by analysis visit and overall of the number of subjects meeting criteria for hypertension based on age, gender, and height-adjusted systolic blood pressure and diastolic blood pressure percentile results [[Flynn 2017](#)].

- Normal BP: BP <90th percentile for age, sex, and height; or <120/<80 mm Hg for adolescents ≥ 13 years old;
- Elevated BP: BP reading ≥ 90 th percentile and <95th percentile for age, sex, and height; or 120 to 129/<80 mm Hg for adolescents ≥ 13 years old;
- Hypertension: BP ≥ 95 th percentile for age, sex, and height; or $\geq 130/80$ mm Hg for adolescents ≥ 13 years old.

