2.6.12. Vital Signs, Height, Weight, and Physical Examination

Vital signs (including systolic and diastolic blood pressure, pulse rate, and body temperature), height, and weight will be monitored at Screening (Visit 1), baseline (Visit 2), Week 12 (Visit 3), Week 24 (Visit 4), Week 36 (Visit 5), Week 48 (Visit 6), Week 60 (Visit 7), and Week 72 (Visit 8), Week 96 (Visit 9), Week 120 (Visit 10), and Week 144 (Visit 11 - End of Treatment/Premature Discontinuation).

A full physical examination (including evaluation of cardiovascular system, chest and lungs, thyroid, abdomen, nervous system, skin and mucosae, musculoskeletal system, eyes, ears, nose, mouth, throat, spine, lymph nodes, extremities, and genitourinary) will be conducted at Screening (Visit 1), Week 72 (Visit 8) and Week 144 (Visit 11 - End of Treatment/Premature Discontinuation).

A symptom-directed physical examination will be conducted at Baseline (Visit 2), Week 24 (Visit 4), and Week 48 (Visit 6).

2.6.13. 12-Lead Electrocardiogram (ECG)

A 12-lead electrocardiogram (ECG) will be obtained at Screening (Visit 1), Week 24 (Visit 4), Week 48 (Visit 6), Week 72 (Visit 8) and Week 144 (Visit 11 - End of Treatment/Premature Discontinuation). The ECG will be performed and interpreted locally. The findings will be captured with the eCRF.

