3.2. As-Treated Population for On-Ataluren Analysis

The as-treated population for open-label analysis (hereafter referred to as as-treated-OA) consists of all randomized subjects who receive at least 1 dose of ataluren anytime during the study. This population will be used for summary and analysis of open-label safety endpoints.

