4. GENERAL CONSIDERATIONS

4.1. Definitions of Treatment Periods

In general, the open-label data analyses will be based on two treatment periods, the overall treatment period and the on-ataluren treatment period.

Overall treatment period: defined as the period from randomization to the end of study, will be used for analyzing and summarizing efficacy endpoints.

On-ataluren treatment period: defined as the period from the first dose of ataluren, regardless of double-blind or open-label ataluren, to the end of the study, will be used for summarizing safety endpoints.

The corresponding baseline for each treatment period is defined in Section 4.3. The corresponding analysis windows are defined in Section 4.9.

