4.3. Baseline and Endpoint Definitions

Two baselines will be used for open-label data analysis, study baseline and on-ataluren baseline.

The study baseline, defined as the last assessment prior to randomization, will be used for analyzing and summarizing efficacy endpoints. Study baseline 6MWD is defined as the maximum measurement of valid Day 1 and Day 2 6MWD values.

The on-ataluren baseline, defined as the last available measurement prior to the first dose of ataluren, will be used for summarizing safety endpoints.

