4.9. Analysis Window

Two sets of analysis windows will be assigned in open-label analyses depending on the treatment period.

Analysis visit windows during overall treatment period will be derived as in [Table 1](#) based on days from randomization to the corresponding visit date. The analysis window during the overall treatment period will be used for efficacy analysis or summaries as appropriate.

Table 1: Analysis Window for Overall Treatment Period

| Analysis Visit | Scheduled Visit Number (study day) | Analysis Window (study day) |
|----------------|------------------------------------|---|
| Week 12 | Visit 3 (85) | [43, 126] |
| Week 24 | Visit 4 (169) | [127, 210] |
| Week 36 | Visit 5 (253) | [211, 294] |
| Week 48 | Visit 6 (337) | [295, 378] |
| Week 60 | Visit 7 (421) | [379, 462] |
| Week 72 | Visit 8 (505) | [463, 546] |
| Week 96 | Visit 9 (673) | [547, 756] |
| Week 120 | Visit 10 (841) | [757, 924] |
| Week 144 | Visit 11 (1009) | Any visit occurred on or after 925 days |

Study day is calculated as visit day – randomization date +1.

Analysis window during on-ataluren treatment period will be derived as in [Table 2](#) based on days from first day of ataluren use to the corresponding visit date. The analysis window during the on-ataluren treatment period will be used for summarizing safety assessments as appropriate.

Table 2: Analysis Window for On-Ataluren Treatment Period

| Analysis Visit for Early-start Ataluren | Scheduled Visit Number (On-ataluren Day) | Analysis Window (On-ataluren days) | Analysis Visit for Delayed-start Ataluren | Scheduled Visit Number (On-ataluren Day) | Analysis Window (On-ataluren days) |
|---|--|---|---|--|--|
| OA Week 12 | Visit 3 (85) | [43, 126] | | | |
| OA Week 24 | Visit 4 (169) | [127, 210] | OA Week 24 | Visit 9 (169) | [2, 253] |
| OA Week 36 | Visit 5 (253) | [211, 294] | | | |
| OA Week 48 | Visit 6 (337) | [295, 378] | OA Week 48 | Visit 10 (337) | [254, 421] |
| OA Week 60 | Visit 7 (421) | [379, 462] | | | |
| OA Week 72 | Visit 8 (505) | [463, 546] | OA Week 72 | Visit 11 (505) | Any On Ataluren visit occurred after 422 OA days |
| OA Week 96 | Visit 9 (673) | [547, 756] | | | |
| OA Week 120 | Visit 10 (841) | [757, 924] | | | |
| OA Week 144 | Visit 11 (1009) | Any visit occurred on or after 925 days | | | |

OA = on-ataluren. On-ataluren day is calculated as visit date – first dose of ataluren date + 1.

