7. SAFETY EVALUATION

The safety evaluations will be summarized by treatment groups and overall during on-ataluren treatment period based on as-treated-OL population using on-ataluren baseline. By-visit summaries will be provided based on the on-ataluren analysis windows.

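### In the open-label SAP, any-time hypertension and laboratory counts would compare arms with unequal numbers of checks (9 against 3 for blood pressure, 6 against 3 for laboratory draws), with no allowance for it

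*SAP*

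**What the plan says.** Section 7 of the open-label SAP sets the frame for all safety tables: "The safety evaluations will be summarized by treatment groups and overall during on-ataluren treatment period". Section 4.1 describes that period as "defined as the period from the first dose of ataluren, regardless of double-blind or open-label ataluren", running to the end of the study. The population (3.2) "consists of all randomized subjects who receive at least 1 dose of ataluren anytime during the study". "The on-ataluren baseline, defined as the last available measurement prior to the first dose of ataluren" (4.3) is the reference value, so the Week 72 visit normally serves as baseline in the delayed-start arm and is not a post-baseline check there.

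Blood pressure is summarized in 7.5: "A summary will also be provided by analysis visit and overall of the number of subjects meeting criteria for hypertension". No rule is given for the *overall* line. For laboratory values, 7.2 states that "the CTCAE grades increase from baseline to Grade 2 or higher grade will be considered as clinically significant (CS) and the incidence will be summarized". The renal-threshold and liver-test summaries in the same section are also taken over all post-baseline results.

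Section 7.1.1 gives exposure-adjusted incidence and event rates for TEAEs. Nothing similar is stated for blood pressure or laboratory abnormalities. Protocol 9.4.7 planned the vital-sign and laboratory summaries by double-blind and open-label phase, and within each phase the two arms follow the same schedule. The move to the on-ataluren period is not among the major changes listed in open-label SAP section 8.

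**The concern.** The share of boys with at least one qualifying value grows with the number of times they are checked, even if the risk at each check is the same. A table that sets the two arms side by side on such a share mixes risk with the number of checks. A reader could take a higher early-start figure as a sign that raised blood pressure or laboratory toxicity accumulates with longer ataluren use, when part or all of the gap may come from the schedule. The column pooling both arms would also combine boys with 3 and 9 scheduled checks. At stake is the reading of descriptive long-term safety tables. No efficacy conclusion and no controlled safety comparison depends on them.

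**Working it through.** **Number of checks.** The documents state no flag rate for these tables. The figure that can be reproduced is the count of visits per arm.

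- Vital signs (open-label SAP 2.6.12) are scheduled in the double-blind period at "Week 12 (Visit 3), Week 24 (Visit 4), Week 36 (Visit 5), Week 48 (Visit 6), Week 60 (Visit 7), and Week 72", then at Weeks 96, 120 and 144. That gives 6 + 3 = 9 checks on ataluren for early start. For delayed start only Weeks 96, 120 and 144 follow the first ataluren dose: 3 checks.
- Laboratory draws (2.6.11) after study baseline are at Weeks 24, 48, 72, 96, 120 and 144: 6 for early start. The last three give 3 for delayed start.
- Section 4.9 ("Analysis window during on-ataluren treatment period will be derived as in" Table 2) agrees. It lists 9 on-ataluren visits for early start and 3 for delayed start (OA Weeks 24, 48 and 72).

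**Formulas.** Let p be the probability that one check qualifies, equal in both arms, and k the number of checks.

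- Independent checks: P(any) = 1 − (1 − p)^k.
- Within-boy correlation ρ (beta-binomial): a = p(1 − ρ)/ρ, b = (1 − p)(1 − ρ)/ρ, and P(any) = 1 − B(a, b + k)/B(a, b).

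Neither p nor ρ is in the documents. Both are assumptions, varied over p = 1% to 20% and ρ = 0 to 0.8.

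**Results at p = 5%.** With independent checks, 1 − 0.95^9 = 37.0%, 1 − 0.95^6 = 26.5% and 1 − 0.95^3 = 14.3%.

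| ρ | Blood pressure, 9 vs 3 | Ratio | Laboratory, 6 vs 3 | Ratio |
|---|---|---|---|---|
| 0 | 37.0% vs 14.3% | 2.59 | 26.5% vs 14.3% | 1.86 |
| 0.3 | 18.9% vs 10.8% | 1.75 | 15.7% vs 10.8% | 1.46 |
| 0.5 | 13.4% vs 8.9% | 1.50 | 11.7% vs 8.9% | 1.31 |
| 0.8 | 7.8% vs 6.5% | 1.21 | 7.3% vs 6.5% | 1.13 |

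Over the whole grid the ratio runs from 2.91 (p = 1%, ρ = 0) down to 1.17 (p = 20%, ρ = 0.8) for blood pressure, and from 1.97 to 1.11 for laboratory values. It stays above 1 throughout, given equal p.

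**What would cancel it.** With independent checks, the shares are equal when the delayed-start per-check risk q satisfies (1 − q)^3 = (1 − p)^9, so q = 1 − (1 − p)^3. For laboratory values, q = 1 − (1 − p)^2. At an early-start p of 5%, q is 14.3% for blood pressure and 9.8% for laboratory values.

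**Which repairs equalize the checks.**

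- Cutting at 72 on-ataluren weeks gives 3 vs 3 laboratory draws but leaves blood pressure at 6 (Weeks 12 to 72) vs 3.
- A rate per patient-year does not fully repair blood pressure, because scheduled exposure differs 2-fold (144/72) and checks 3-fold (9/3).
- Restricting to OA Weeks 24, 48 and 72 gives 3 vs 3 for both measures, and at equal p the expected shares are the same.
- The windows need aligning too. Table 2 sets OA Week 24 at days 127 to 210 for early start but days 2 to 253 for delayed start.

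**The case against.** Most of the opposing argument limits the point rather than removing it.

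- **The any-time rule is not written down.** In section 7 the word *overall* means the arms pooled; in 7.5 it stands beside *by analysis visit* without a definition. The table shells are in a separate document. A reader might infer that the SAP explicitly counts a boy once if he is ever flagged, but it does not say so. That reading is the natural one in 7.5. For laboratory values it is better supported, by the all-post-baseline wording and by the worst-grade rule in Protocol 9.4.7. If something else is meant, the term still needs a definition.
- **Much is already unaffected.** Hypertension is also shown by visit, and OA Weeks 24, 48 and 72 are labelled in both arms. Laboratory shift tables and last-assessment summaries do not grow with the number of checks. Treatment duration is tabulated (5.2). The double-blind SAP supplies the controlled comparison on equal schedules, and no between-arm safety test is planned.
- **The hypertension event of special interest is separate.** Section 7.1.2 defines it from reported adverse events with concomitant corticosteroids, not from the percentile counts in 7.5, and TEAEs already receive exposure-adjusted rates. A reader might infer that this event is distorted by the *overall* count; the documents do not support that.
- **A full-period count is legitimate for uncommon toxicity.** Replacing it with matched visits would lose late and unscheduled abnormal values. Protocol Table 2 allows immediate confirmation of renal abnormalities, and 7.2 plans no by-visit table of Grade 2 or higher, renal-threshold or liver-test incidence that would retain them. This stands, and it is why the full-period counts should be kept.

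What remains is that the between-group any-time counts have no allowance for unequal checks, while the TEAE tables do allow for unequal exposure.

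**Conclusion.** The point holds in a limited form. On the natural reading, the *overall* hypertension count and the Grade 2 or higher, renal-threshold and liver-test incidences compare arms with 9 against 3 and 6 against 3 scheduled checks. At equal per-check risk the early-start share is expected to be higher. How much higher depends on p and the within-boy correlation, neither of which the documents give. Repeated readings in one boy are likely to be correlated, so the independent figures are best read as the upper end of the range at a given p.

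A reader might go further and conclude that early start must look worse. The documents do not support that. Delayed-start boys are about 72 weeks older at their on-ataluren baseline, and a higher per-check risk in them could offset or reverse the gap. The counts are also of scheduled visits; dropout and unscheduled tests would change them. The tables are descriptive, so this is a matter of clear definition and fair presentation.

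**What to change.** In open-label SAP 7.5 and 7.2:

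1. Define *overall*, and the laboratory incidences, as any qualifying post-baseline value in the on-ataluren period.
2. Keep the full-period counts, including unscheduled values, as descriptive within-arm figures. Label them with follow-up time and number of readings per arm.
3. For the between-group comparison, add a count restricted to the shared scheduled visits OA Weeks 24, 48 and 72, with one common set of windows for both arms. Alternatively, report the percentage of readings that qualify, with the number of readings as denominator.

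This needs SAP wording and one extra table per parameter, and no new data. The matched count uses fewer early-start readings (3 of 9 for blood pressure, 3 of 6 for laboratory draws) and is less precise for that arm, but the full-period count beside it retains every value.

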8. CHANGES FROM THE PROTOCOL

Major changes to the planned analyses from the protocol are summarized as follows:

- NSAA total score will be calculated as the sum of the 16 scores (except for lifts head), instead of 17, based on Mayhew's publication [Mayhew 2013a].
- Slope of change in 6MWD over 144 weeks is removed from the list of secondary endpoints in section 2.3.2.
- Modified Intention-to-Treat (mITT) Population is removed from the list of study populations
- MMRM model was modified from a linear regression model to a MMRM model with visit time as a categorical variable to account for the nonlinearity of study data.

9. VERSION HISTORY

This Statistical Analysis Plan (SAP) for study PTC124-GD-041-DMD is based on protocol version 4.0 (dated 21JUL2020).

| SAP Version | Approval Date | Description |
|-------------|---------------|---|
| 1.0 | 04APR2022 | Original version |
| 2.0 | 25SEP2023 | 
Summary of Changes:
 
To be aligned with the “Changes from Planned Analysis” SAP for the double-blind period:
 
1) mITT population removed throughout this SAP2) MMRM slope model replaced with MMRM categorical model as primary analysis method3) slope of change in 6MWD over 144 weeks removed from the list of secondary endpoints4) baseline disease severity category updated throughout this SAP 
Other changes:
 
5) analyses on time to 10% persistent worsening and 30meter drop from baseline in 6MWD were added as sensitivity analyses |

11. TABLE OF CONTENTS FOR TABLES, FIGURES, AND LISTINGS

The tables, listings, and graphs shells for the study will be provided in a separate document.

APPENDIX 1. SCHEDULE OF ASSESSMENTS

| Study Period | | Screening | Double-Blind Treatment | | | | | | | | Notes |
|---|--|-----------|------------------------|----|-----|-----|-----|-----|-----|---|--|
| Study Week | | -2 weeks | 1 | 12 | 24 | 36 | 48 | 60 | 72 | 2-week screening period may be extended by 1 week if necessary to schedule pretreatment MRI | |
| Study Day | | | 1 | 84 | 168 | 252 | 336 | 420 | 504 | | |
| Visit Window (days) | | | | ±7 | ±7 | ±7 | ±7 | ±7 | ±7 | | |
| Visit Number | | 1 | 2 | 3 | 4 | 5 | 6 | 7 | 8 | At Visit 2, complete assessments before first dose | |
| Visit Day | | | 1 | 2 | | | | | 1 | 2 | 2-day visits only at Visit 2 and Visit 8 |
| Informed consent | | X | | | | | | | | | May be obtained prior to Visit 1 (eg, by phone) |
| Enter subject in IRT system | | X | | | | | | | | | Access IRT system to enter subject |
| Clinical and medication history | | X | | | | | | | | | |
| Hepatitis screen | | X | | | | | | | | | |
| Urinalysis sample | | X | X | | X | | X | | X | | |
| EQ-5D and DMDSAT | | X | X | | X | X | X | X | X | | Provided to subject at Visit 1 for at-home completion between visits and reviewed for compliance in clinic |
| DMD Upper Limb PROM | | | X | | X | X | X | X | X | | Performed only in subjects ≥7 years at baseline |
| Height | | X | X | | X | X | X | X | X | | |
| Weight | | X | X | | X | X | X | X | X | | |
| Physical examination | | X | X | | | X | | X | | X | Full (Visit 1, 8) or symptom-directed (Visit 2, 4, 6) |
| Concomitant medications | | X | X | | X | X | X | X | X | | |
| Adverse events | | X | X | | X | X | X | X | X | | |
| Genotyping sample | | | X | | | | | | | | |
| Hematology sample | | X | X | | X | | X | | X | | |
| Biochemistry sample | | X | X | | X | | X | | X | | To be collected in fasted state (except Visit 1) |
| Vital signs | | X | X | | X | X | X | X | X | | |
| Myometry | | X | X | | X | X | X | X | X | | Performed only in subjects <7 years at baseline |
| PUL | | X | X | | X | X | X | X | X | | Performed only in subjects ≥7 years at baseline |
| 6-minute walk test (1 st test) | | X | X | | X | X | X | X | X | | |
| 6-minute walk test (2 nd test) | | | | X | | | | | | X | |
| NSAA | | X | X | | X | X | X | X | X | | |

| Study Period | | Screening | Double-Blind Treatment | | | | | | | | Notes | |
|-----------------------|--|-----------|------------------------|----|-----|-----|-----|-----|-----|---|-------|---|
| Study Week | | -2 weeks | 1 | 12 | 24 | 36 | 48 | 60 | 72 | 2-week screening period may be extended by 1 week if necessary to schedule pretreatment MRI | | |
| Study Day | | | 1 | 84 | 168 | 252 | 336 | 420 | 504 | | | |
| Visit Window (days) | | | | ±7 | ±7 | ±7 | ±7 | ±7 | ±7 | | | |
| Visit Number | | 1 | 2 | 3 | 4 | 5 | 6 | 7 | 8 | At Visit 2, complete assessments before first dose | | |
| Visit Day | | | 1 | 2 | | | | | | 1 | 2 | 2-day visits only at Visit 2 and Visit 8 |
| Timed function tests | | X | X | | X | X | X | X | X | X | | |
| Study drug dispensed | | | | X | X | X | X | X | X | | X | Open-label study drug dispensed at Visit 8 |
| Study drug compliance | | | | | X | X | X | X | X | X | | |
| 12-lead ECG | | X | | | | X | | X | | X | | |
| Spirometry | | X | X | | | | | | | X | | Required at all visits after subject loses ambulation |
| Echocardiogram | | X | | | | | | | | X | | |
| Randomization | | | | X | | | | | | | | Access IRT system to randomize subject |
| Upper leg imaging | | | X | | | X | | X | | X | | Performed only at pre-qualified sites. May be done between Visits 1 and 2 (pre-treatment assessment) or ±4 weeks of visit (post-treatment assessments). |

Abbreviations: DMD = Duchenne Muscular Dystrophy, DMDSAT = DMD Functional Ability Self-Assessment Tool, ECG = electrocardiogram, EQ-5D = EuroQoL 5-Dimension, IRT = interactive response technology, NSAA = North Star Ambulatory Assessment, PROM = Patient-Reported Outcome Measure, PUL = Performance of Upper Limb

| Study Period | Open-Label Treatment | | | Follow-Up | Notes |
|-------------------------|----------------------|-----|-----|---------------|--|
| Study Week | 96 | 120 | 144 | 148 | |
| Visit Window (days) | ±7 | ±7 | ±7 | ±7 | |
| Visit Number | 9 | 10 | 11 | 12 (by phone) | Subjects who discontinue prematurely should complete Visit 11 and Visit 12 (by phone) |
| Urinalysis | X | X | X | | |
| EQ-5D and DMDSAT | X | X | X | | Provided to subject at Visit 1 for at-home completion between visits and reviewed for compliance in clinic |
| DMD Upper Limb PROM | X | X | X | | Performed only in subjects ≥7 years old at baseline |
| Height | X | X | X | | |
| Weight | X | X | X | | |
| Physical examination | | | X | | Full (Visit 11) |
| Concomitant medications | X | X | X | X | |
| Adverse events | X | X | X | X | |
| Hematology sample | X | X | X | | |
| Biochemistry sample | X | X | X | | To be collected in fasted state |
| PK sample | | | X | | Pre-morning dose and 2 hours post-morning dose |
| Vital signs | X | X | X | | |
| PUL | X | X | X | | Performed only in subjects ≥7 years old at baseline |
| Myometry | X | X | X | | Performed only in subjects <7 years old at baseline |
| 6-minute walk test | X | X | X | | |
| NSAA | X | X | X | | |
| Timed function tests | X | X | X | | |
| Study drug dispensed | X | X | | | Open-label study drug dispensed at Visit 8 |
| Study drug compliance | X | X | X | | |
| 12-lead ECG | | | X | | |
| Spirometry | | | X | | Required at all visits after subject loses ambulation |
| Echocardiogram | | | X | | |
| Upper leg imaging | | | X | | Performed only at pre-qualified sites. May be assessed ±4 weeks of visit date |

Abbreviations: DMD = Duchenne muscular dystrophy, DMDSAT = DMD Functional Ability Self-Assessment Tool, ECG = electrocardiogram, EQ-5D = EuroQoL 5-Dimension, NSAA = North Star Ambulatory Assessment, PK = pharmacokinetic; PROM = Patient-Reported Outcome Measure, PUL = Performance of Upper Limb

